## 4.2 Handling of dropouts or missing data

### 4.2.1 Handling of missing data in seizure frequency

Unless noted otherwise, the imputation described below will be applied to seizure frequency. The responder status will be determined based on the imputed seizure frequency data. Sensitivity analyses for missing data are described in Section 8.1.2 for the primary efficacy variable.

#### 4.2.1.1 Missing data caused by missing seizure diary

Seizure frequency will be computed over non-missing diary days. Diary compliance evaluation is described in Section 7.2. Subjects with diary data deemed unacceptably incomplete (during blinded data review) for the primary efficacy variable will be excluded from the PPS. If seizure type is known but the number of seizures is unknown, the number of seizures will be imputed using the median for the same seizure type (daily seizure number > 0) during the same analysis period (baseline or treatment period). Otherwise, the missing seizure number will be imputed using the count of next higher level of seizure type.

#### 4.2.1.2 Missing seizure data caused by discontinuation

- Seizure frequency by analysis period:

For subjects who prematurely discontinued during the Treatment Period, the calculation of 28-day adjusted seizure frequency over the Treatment Period will be based on available seizure diary up to the end of the Treatment Period.

If a subject had less than 14 days of seizure data during the Titration and Stabilization Period, seizure frequency during the Treatment Period will be calculated based on the last 28 days with seizure data, including the data in the Baseline Period. For subjects who prematurely discontinued the study, the following methods will be applied to obtain a seizure frequency estimate for the Maintenance Period:

- Subjects who discontinued during the Titration and Stabilization Period: If a subject had at least 14 days of seizure data, seizure frequency will be calculated using all available data in the Titration and Stabilization Period and carry forward for the Maintenance Period. If a subject had less than 14 days of seizure data, seizure frequency will be calculated based on the last 28 days with seizure data, including the data in the Baseline Period and carry forward for the Maintenance Period.
  - Subjects discontinued during the Maintenance Period: If a subject had at least 28 days of seizure data during the Maintenance Period, seizure frequency will be calculated using all available data in the Maintenance Period. If a subject had less than 28 days of seizure data during the Maintenance Period, seizure frequency will be calculated based on the last 28 days with seizure data, including the data in the Titration and Stabilization Period.
- Seizure frequency by 4-week interval

Seizure frequency by 4-week interval will be calculated for the sensitivity analyses (Section 8.1.2.2) and secondary efficacy analyses (Section 8.3.2.1). Seizure frequency during a 4-week interval will be calculated as long as seizure data are available for at least 1 day in the given interval. No imputation will be applied for discontinuations.

## **4.2.2 Handling of missing data for adverse events and concomitant medications**

For analyses of AEs and concomitant medication usage, a complete date must be established to correctly identify the AE or medication as occurring during treatment or not. In the event of completely missing dates, or if ambiguity or incomplete data makes it impossible to determine whether a medication was concomitant, or an adverse event was treatment emergent, the medication will be considered as concomitant or the adverse event will be considered treatment emergent.

For purposes of imputing missing components of partially-reported start and stop dates for AEs and for medication use, the algorithms listed below will be followed. Start and stop dates of AEs or concomitant medication will be displayed as reported in the subject data listings (i.e., no imputed values will be displayed in data listings).

Partial AE and concomitant medication start dates will be imputed as described in the following sections.

### **4.2.2.1 Imputation of Partial Start Dates**

- If only the month and year are specified and the month and year of first dose of IMP is not the same as the month and year of the start date, then use the 1st of the month
- If only the month and year are specified and the month and year of first dose of IMP is the same as the month and year of the start date, then use the date of first dose of IMP
- If only the year is specified, and the year of first dose of IMP is not the same as the year of the start date, then use the 1st of January of the year of the start date
- If only the year is specified, and the year of first dose of IMP is the same as the year of the start date, then use the date of first dose
- If the start date is completely unknown and the stop date is unknown or not prior to the date of first dose of IMP, then use the date of first dose of IMP.
- If the imputed start date is after the known stop date, set the start date to be the same as the stop date.

### **4.2.2.2 Imputation of Partial Stop Dates**

- If only the month and year are specified, then use the last day of the month
- If only the year is specified, then use December 31st of that year
- If the stop date is completely unknown, do not impute the stop date

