### **2.6.2 Study duration per subject**

The total duration of study per subject will be up to 27 weeks with a maximum of 19 weeks exposure to PSL. An additional follow-up echocardiogram will be performed at 6 months ( $\pm 1$  month) after the last IMP intake only for subjects exposed to IMP for more than 3 weeks and either discontinuing the study or not entering the OLE.

The end of the study is defined as the date of the last SFU Visit (30-days after the last IMP intake) of the last subject in the study. Additionally, the reporting of SAEs will continue until the 6-month follow-up echocardiogram.

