- Summary of the duration in days per event for the following TEAEs: somnolence, dizziness, fatigue, irritability and headache. In this analysis, if an AE is ongoing, the duration will be calculated till the date of final contact.

Summaries will be presented based on standard Sponsor AE table formats and considering formats used for the PSL program.

Where dates are missing or partially missing, AEs will be assumed to be treatment-emergent, unless there is unmistakable evidence (through comparison of partial dates, see Section 4.2) to suggest that the AE started prior to the first dose of study treatment. Summary tables will contain counts of subjects, percentages of subjects in parentheses and the number of events where applicable. A subject who has multiple events in the same MedDRA category (SOC or PT) will be counted only once in the subject count for that category, however all events will be included in the event count for the category. In summaries including relationship to study treatment, the following relationships will be summarized: 'Not related', 'Related'. A subject may be counted more than once according to the relationship to study treatment. Events with missing relationship will be considered as 'Related' to the last given study product for summary purposes but recorded as missing in the listings. In summaries of the maximum intensity, the following intensity categories will be summarized: 'Mild', 'Moderate', 'Severe'. Subjects who experience the same event multiple times, with differing severities, will be included in the most severe category. Events with missing intensity will be considered as 'Severe' events for summary purposes but recorded as missing in the listings. The main reasons for treatment discontinuation will be listed by subject. The daily dose of study medication corresponding to the AE onset date will be included in the listing. Daily dose will be derived from 'Study Medication Administration' CRF.

Adverse event summaries will be ordered in terms of decreasing frequency for SOC, and PT within SOC, within the PSL total group column.

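### Partial AE stop dates are imputed to month-end or 31 December with no cap, so in the duration summary a resolved event can be given more days than an ongoing one

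*SAP*

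**What the plan says.** SAP 4.2.2 brings adverse events within the partial-date rules: "For purposes of imputing missing components of partially-reported start and stop dates for AEs and for medication use, the algorithms listed below will be followed". SAP 4.2.2.2 then gives three stop-date rules:

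- Month and year known: "If only the month and year are specified, then use the last day of the month".
- Year only: "If only the year is specified, then use December" 31 of that year.
- Nothing known: "If the stop date is completely unknown, do not impute the stop date".

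None of these is limited by final contact, study termination or data cut-off, and no other section supplies a limit. The start-date rules in SAP 4.2.2.1 do carry a consistency check: "If the imputed start date is after the known stop date, set the start date to be the same as the stop date".

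Among the outputs for events in the Treatment Period, SAP 10.2 lists: "Summary of the duration in days per event for the following TEAEs: somnolence, dizziness, fatigue, irritability and headache". For that output it adds: "if an AE is ongoing, the duration will be calculated till the date of final contact". SAP 2.6.2 gives the length of the study: "The total duration of study per subject will be up to 27 weeks".

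**The concern.** The two rules put events in the wrong order. An unresolved event stops accruing days at final contact. An event known to have resolved, but with an incomplete stop date, can go on accruing days to the end of that month or year, beyond the last day on which the subject was seen. Of two events with the same onset, the one that ended can be recorded as the longer.

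The summary covers the only five terms given a duration analysis. Protocol 2.3.1 names the same five as the most frequent events in the earlier Phase 2 study. SAP 3.1 reports the mean, SD, minimum and maximum as well as the median, and a single very long record can move the mean, SD and maximum. Under SAP 4.2.2 the listings show dates as reported, so a reader could not find the imputed stop date there.

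**Working it through.** **Inputs.** The stop-date rules are from SAP 4.2.2.2 and the ongoing-event rule from SAP 10.2. Period lengths are from SAP 2.6.1 and 2.6.2. SAP 10.2 gives no duration formula, so I assume stop − start + 1, the form SAP 10.1 uses for exposure. Calendar dates are illustrative.

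**Study length.** The stated maximum is 27 × 7 = 189 days. From its parts: 4 + 16 + 3 = 23 weeks = 161 days, plus 30 days to the safety visit = 191 days, or 27.3 weeks. This agrees with the stated figure. First dose to final contact is (16 + 3) × 7 + 30 = 163 days.

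**Worked case.** First dose is 1 January 2019, so final contact is 12 June 2019 (day 163 of the year). Onset is 15 January (day 15).

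- Ongoing: 163 − 15 + 1 = 149 days.
- Resolved, stop reported as 2019: 365 − 15 + 1 = 351 days. This is 202 days more than the ongoing event and 162 more than 189.
- Resolved, stop reported as June 2019: 181 − 15 + 1 = 167 days, 18 more than the ongoing event.

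**Other cases.**

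| Case | Ongoing | Month of final contact | Year of onset |
|---|---|---|---|
| First dose 1 Feb 2019, onset 10 Feb, final contact 13 Jul | 154 | 172 | 325 |
| Same onset, last dose Day 14, final contact 16 Mar | 35 | 50 | 325 |
| First dose 1 Oct 2019, onset 10 Oct, final contact 11 Mar 2020 | 154 | not shown | 83 |

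The last row shows that the year-only rule does not always overrun. If 31 December comes before final contact, there is no excess.

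**Limits of the month rule.** When the stop month is the month of final contact, the excess is the last day of the month minus the day of final contact, so at most 31 − 1 = 30 days. Even with Day 1 onset the longest result is 163 + 30 = 193 days. Durations beyond the study therefore come almost entirely from year-only dates.

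**How far the year rule depends on the calendar.** I took every first-dose date in a year, with onset on Day 10, full follow-up, and the stop year equal to the onset year. The imputed duration exceeds the ongoing one for about 58% of first-dose dates and exceeds 189 days for about 48%. The largest overrun is 211 or 212 days, depending on the year. These are shares of calendar dates under those assumptions, not a forecast of how many records are affected.

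**With the cap.** The 351 and 167 days both become 149. In the table, 325 and 172 become 154 in the first row, 325 and 50 become 35 in the second, and 83 stays at 83.

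**The case against.** The strongest defence is that SAP 4.2.2 introduces date imputation to decide whether an event or medication fell within treatment. The latest possible stop date is a cautious choice for that. SAP 10.2 does not say that imputed stops enter the duration summary. This is fair, but SAP 4.2.2.2 is the only rule for a partial adverse event stop date, so a programmer following the plan would use it. The SAP also bounds dates elsewhere: imputed starts in 4.2.2.1, absences in 8.3.2.25 and last dose in 10.1. The missing bound looks like an omission.

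The second defence is that little depends on it. Duration is not among the safety variables in SAP 2.4, the output is descriptive, and a stray record barely moves the median. Events are prompted for at each visit and recorded at every visit and call, and data are cleaned and reviewed before lock, so year-only stops should be uncommon. All of this stands and keeps the point minor.

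A reader might infer more than the documents support:

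- **A typical overrun or a shift in the mean.** Either needs the number of partial dates, the number of events per term and the distribution of true stop dates. None is given.
- **A bias between arms.** Nothing suggests that partial dates differ by arm in this blinded trial.
- **That any duration above 189 days is impossible.** Protocol 11.1.3 allows events ongoing at study end to be followed to resolution, so a genuine stop can fall after final contact.
- **That a cap would guarantee no resolved event exceeds an ongoing one.** For the same reason it would not. A real, fully reported late stop date can still do so.

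**Conclusion.** The point holds as a minor defect in one descriptive table. Followed as written, the plan can give a resolved event with a partial stop date more days than an identical ongoing event. The excess is up to 30 days for a stop in the month of final contact and several months for a year-only stop, which can exceed the nominal study length. This rests on two readings: that imputed stops feed the SAP 10.2 summary, and that duration counts both end days. The effect on the reported mean, SD and maximum is unknown because the number of partial stop dates is unknown. Efficacy results and adverse event incidences do not depend on it.

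**What to change.** Add one clause for the duration summary, in SAP 10.2 or as a qualified line in SAP 4.2.2.2. When final contact falls in the reported stop month or year, the imputed stop is the earlier of period-end and final contact. Leave fully reported stop dates unchanged, and also partial dates in a month or year after final contact, because Protocol 11.1.3 makes both legitimate. Say explicitly that imputed stop dates are used in this summary, and give the duration formula.

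The summary is confined to events in the Treatment Period, so the cap cannot place a stop before onset. Treatment-emergent and concomitant-medication classification is untouched. The cost is one SAP clause and one line of programming, with no new data.

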## **4.2.3 Handling of missing data for history of epileptic seizures and diagnosis of epilepsy**

### **4.2.3.1 Incomplete dates for first epileptic seizure**

To calculate the time since the first seizure relative to the date of Visit 1 or age at onset of first seizure, January 1st of the year will be imputed for the date of birth, as only year of birth is collected on CRF. And a complete date will be imputed for partially missing first seizure date as following:

- Missing the day, but month and year present, then assign the 1st day of the month.
- Missing the day and month, but year present, then assign January 1st of the year.
- Completely missing, no imputation will be done.

#### **4.2.3.2 Incomplete dates for last epileptic seizure**

To calculate the time since last seizure relative to the date of Visit 1, a complete date will be imputed for partially missing last seizure date as following:

- Missing the day, but month and year present, then assign the 1st day of the month.
- Missing the day and month, but year present, then assign January 1st of the year or Visit 1, whichever is later in the year.
- Completely missing, no imputation will be done.

#### **4.2.3.3 Incomplete dates for first epilepsy diagnosis**

Month and year of the first epilepsy diagnosis are collected on the CRF. To calculate the duration of epilepsy derived from the date of first diagnosis relative to the date of Visit 1, or age at epilepsy diagnosis, January 1st of the year will be imputed for the date of birth, as only year of birth is collected on CRF. And a complete date will be imputed for partially missing date of the first epilepsy diagnosis as following:

- Month and year present, then assign the 1st day of the month or the date of the first seizure, whichever is later in the month.
- Missing the month, but year present, then assign January 1st of the year or the date of the first seizure, whichever is later in the year.
- Both month and year are missing, no imputation will be done.

### **4.3 Interim analyses and data monitoring**

There is no formal interim analysis planned for the study.

A Data Monitoring Committee (DMC) will be formed to monitor the ongoing safety of the study through periodic review of data summaries. The general scope of DMC activities is presented in the protocol and will be described in detail in a separate DMC Charter. Preparation of data summaries for review by the DMC will be described in a separate DMC SAP.

### **4.4 Multicenter studies**

In general, efficacy and safety summaries and analyses will be presented across investigative sites, countries and regions. When applicable, analyses will include adjustment for region, which is one of the stratification factors.

### **4.5 Multiple comparisons/multiplicity**

For the primary efficacy variables, statistical testing will be based on the comparison of 400mg bid, 200mg bid and 100mg bid PSL groups versus placebo. Type 1 error will be controlled by the Hochberg step-up procedure within SAS® Proc Multtest. Hochberg procedure orders the p-values from the largest to the smallest. The significance level for the k-th step is given by 0.05/k. More specifically, the largest p-value will be compared to 0.05. If it is smaller than 0.05, we will stop the testing and conclude significance for all 3 comparisons; otherwise we will move to the

second highest p-value. The second largest p value will be compared to 0.025 ( $=0.05/2$ ). If it is smaller than 0.025, we will stop and conclude significance for this comparison and the subsequent one that produced p-values smaller than the current one; otherwise we will move to the smallest p-value. The smallest p-value will be compared to 0.0167 ( $0.05/3$ ). If it is smaller than 0.0167, we will conclude a significant difference between the dose and the placebo; otherwise, stop and no comparison is significant.

If the 3 higher doses are all statistically different from the placebo, the 50mg bid PSL group will be compared to placebo. Because this follows a gatekeeping procedure, testing will be conducted at the 0.05 level (2-sides). If the p-value is smaller than 0.05, we will conclude 50mg bid is also significantly different from the placebo.

#### **4.6 Use of an efficacy subset of subjects**

The FAS will be used as the primary analysis set for all efficacy analyses. Analyses using the PPS will also be performed for the FDA and European agency primary efficacy variables. The PPS analyses will provide additional information on efficacy evaluations and will describe findings in a subset of subjects who adhered more closely to the study protocol. No other efficacy subsets are defined for statistical analyses.

#### **4.7 Active-control studies intended to show equivalence**

This study is not an active controlled study intended to show equivalence.

#### **4.8 Examination of subgroups**

The primary efficacy variable will be evaluated for subgroups of interest including:

- Age (18 to <65 years,  $\geq 65$  years): less than 5 subjects in  $\geq 65$  years subgroup in the FAS at each treatment group, therefore the subgroup analysis will be omitted.
- Gender
- Region (Europe, North America, and Asia): To ensure at least 5 subjects in each region in the FAS at each treatment group, Asia (Japan) will be pooled with North America. The subgroup analyses will be performed for Europe vs non-Europe.
- Use of AEDs with binding to synaptic vesicle 2A (SV2A) proteins (levetiracetam [LEV] or brivaracetam [BRV], Y/N).

These evaluations will be descriptive; no statistical testing of treatment-by-subgroup interactions nor statistical testing of treatment effects within subgroups will be carried out. No subgroup evaluations are planned for safety variables.

### **5 STUDY POPULATION CHARACTERISTICS**

#### **5.1 Subject disposition**

Screen failure data of screened subjects who did not meet study eligibility criteria are collected on the Study Termination Screen Failure CRF (dates of screen failure and last contact and reason for screen failure).

Disposition data of randomized subjects are obtained from the Study Termination CRF. Variables include date of last administration of study medication, date of premature study

termination, date of final contact with subject, subject status at study termination, primary reason for premature study termination (as listed on the CRF), and if the study blind was broken (Y/N and date, if applicable).

Disposition of subjects (ES) will be listed by region, country and investigative site. A listing will also be provided for study discontinuation (RS), and for study visit dates (RS).

Summaries of the numbers of screened subjects and reasons for screen failures will be produced overall for the ES.

The disposition of the ES will be summarized overall and by region, country and site presenting the dates of first subject in (first enrolled) and last subject out, number of subjects screened, and number of subjects included in the each of the RS, FAS, SS, PPS, and PK-PPS.

The disposition of the SS will be presented as the number and percentage of subjects who completed the study and of subjects who discontinued the study, including a breakdown of the primary reason for discontinuation. Of note, the corresponding table is required for data transparency reporting. Subjects who enrolled into EP0093 will also be summarized. The number of subjects completing and discontinuing with associated reasons for discontinuation at each visit of the Titration and Maintenance Periods will be displayed for the SS.

In addition, the numbers and percentages of subjects (SS) entering and completing each of the following analysis periods: (Titration and Stabilization Period, Maintenance Period, Conversion Period, and Taper and SFU Period) will be summarized by treatment group and overall. The same summary will be repeated by region.

The number and percentage of subjects in the SS who discontinued due to AE categorized by serious fatal, non-fatal, and non-serious fatal AE incidence will also be presented by treatment group and overall. Of note, the corresponding table is required for data transparency reporting.

